STATISTICAL ANALYSIS PLAN FOR
“The Effect of Physician Ownership on Dialysis Outcomes”

PROTOCOL ID: HS-18-00530-1

SECONDARY ID: K08DK118213

Version #2

Last Modified: 3/11/2021

PI: [name], MS

Keck School of Medicine of the University of Southern California

ANALYTIC DATASETS

Facility level dataset

- 1) Merge the physician ownership dataset with DFC
 - a. Primarily use 2017 data, but if a facility is missing data, salvage with 2018, 2016, 2015 years
- 2) Merge zip codes with census / ACS characteristics
- 3) Merge with the facility survey (from 2017)
- 4) Restrict to free-standing facilities where $\leq 15\%$ of patients in 2017 were pediatric (< 18 years old)
- 5) Variables of interest
 - a. Facility Characteristics
 - i. Profit status
 - ii. Chain vs. independent
 - iii. Size of facility (Number of patients)
 - iv. Staff : patient ratio
 - v. ESRD Network
 - b. Outcomes
 - i. All quality measures from DFC dataset
- 6) Get distribution of patient characteristics for each facility
 - a. Link each facility to a patient
 - i. To assign a patient to a facility, first identify all dialysis patients with at least one month of dialysis in all of 2017 and meeting all of the following criteria
 1. Adults with valid 2728 form
 2. In the USA.
 3. Has Medicare FFS for that month of dialysis
 - ii. If a patient has multiple facilities, assign that patient to the facility that holds the plurality share
 - iii. If there are still ties in facilities, use the first observed facility that has the plurality
 - b. For each patient, for the first observed month of dialysis, get:
 - i. Age, Gender, Race, Ethnicity, Payer, Dual-Eligible (if Medicare)
 - ii. Dialysis modality
 - iii. (Do not exclude any patients for this analysis)
 - c. Collapse back to the facility level, and get counts and % by patient characteristic (for continuous variables like age, we use age brackets, i.e., 18-44, 45-54, 55-64, 65-74, 75+)

Patient-month level dataset / inclusion criteria

- 1) This will be a patient-month dataset
- 2) Identify all patients with at least one month of dialysis in 2017 (Jan-Dec)
- 3) Inclusion criteria
 - a. USA
 - b. Adult in the current month
 - c. Valid 2728 form (2005, 2015 form)

- d. Dialyzing in free-standing facility that has fewer than 15% pediatric
 - i. Only keep if patient can be linked to a valid facility survey and can be linked to the ownership dataset
- 4) Must have Medicare FFS in the current month of dialysis

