 - a. Must have at least 12 months of Medicare FFS prior to the current month
 - b. Create indicator variable for whether the patient-month has had 36+ months of Medicare FFS
- 5) Get patient comorbidities using the CCW algorithm
 - a. Use diagnosis codes from claims in a 12 month lookback
 - b. Sensitivity analysis: use diagnosis codes from claims in a 36 month lookback
- 6) Get the zipcode of residence for that month and merge with the ACS to get zipcode characteristics
- 7) Merge with facility file to get facility characteristics + DFC outcomes (we call these facility level outcomes)
- 8) Covariates of interest:
 - a. Patient level
 - i. Age
 - ii. Sex
 - iii. Race
 - iv. Ethnicity
 - v. Whether patient had a transplant previously
 - vi. Whether the patient is incident (within the first 120 days of ESRD)
 - vii. Number of years with ESRD
 - viii. Comorbidities using CCW algorithm
 - b. Facility characteristics
 - i. Profit status
 - ii. Chain vs. independent
 - iii. Size of facility (Number of patients)
 - iv. Staff : patient ratio
 - v. ESRD Network
 - c. Zipcode Characteristics
 - i. Median income
 - ii. High school graduation rate
 - iii. % below poverty
 - d. Monthly level fixed effects (an indicator for each month of the year)
- 9) Patient Level Outcomes
 - a. Whether patient using home dialysis in the month
 - b. Whether patient was receiving dialysis optimally (defined as either peritoneal dialysis, or hemodialysis through an AV fistula or graft)
 - i. Whether patient was using a fistula
 - ii. Whether patient was using a catheter for 3+ months, including the current month (i.e., look back two months to see whether the patient used a catheter in the other two months)
 - c. Get crownweb outcomes (merge with the crownweb dataset by month/year)
 - i. Create an indicator for whether crownweb data missing for that month
 - ii. Hemoglobin < 10

- iii. Hemoglobin > 12
- iv. Calcium > 10.2
- v. Phosphorus > 7
- d. Get other outcomes
 - i. Whether patient died in that month
 - ii. Whether patient was hospitalized that month
 - iii. Whether patient had a hospitalization that month followed by a 30-day readmission
 - 1. Patients are eligible for this only if the patient was discharged alive
 - iv. Whether patient had a hospitalization that month followed by an unplanned 30-day readmission

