 - a. Facility level outcomes as specified above
- 3) Independent Variables:
 - a. Whether facility is physician owned

- b. Regression 1: Control only for facility, geographic, and temporal level covariates
- c. Regression 2: Control for patient, facility, geographic, temporal level covariates.
- 4) Models: OLS for continuous outcomes, logit for binary outcomes, robust standard errors

Patient Level Regressions

- 1) Population: patient-month dataset
- 2) Dependent variable (left hand side):
 - a. Patient level outcomes
- 3) Independent variables (right hand side)
 - a. Whether patient is dialyzing in a facility that is physician owned (covariate of interest)
 - b. Covariates above (patient, facility, zipcode, temporal characteristics)
- 4) Models (in order) for all outcomes except blood transfusion and ESA outcomes:
 - a. Logit with patient level fixed effects, non-parametric bootstrap standard errors
 - b. Logit with patient level fixed effects, robust standard errors
 - c. OLS with patient level fixed effects, cluster robust standard errors at facility level
 - d. OLS with patient level fixed effects, robust standard errors
- 5) Models (in order) for whether patient received a blood transfusion
 - a. Outcomes
 - i. Criteria 1 only
 - ii. Criteria 1+2
 - iii. Criteria 1+2+3
 - b. Models
 - i. Logit with patient level fixed effects, non-parametric bootstrap standard errors
 - ii. Logit with patient level fixed effects, robust standard errors
 - iii. OLS with patient level fixed effects, cluster robust standard errors at facility level
 - iv. OLS with patient level fixed effects, robust standard errors
- 6) Models (in order) for # of units of blood transfused
 - a. Outcomes
 - i. Use the number of units of blood detected under Criteria 1. If a blood transfusion detected under Criteria 2 or 3, indicate that the patient received 1 unit of blood
 - ii. Use the number of units of blood detected under Criteria 1. If a blood transfusion detected under Criteria 2 or 3, indicate that the patient received 1 unit of blood. Also include an indicator variable that the patient had a blood transfusion detected under criteria 2 or 3.

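### Every patient-level model carries patient fixed effects, so the ownership effect rests only on patients whose ownership status changes during 2017, and the fixed-effects logit for death has no finite estimate

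*SAP*

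**What the plan says.** The SAP's patient-month dataset covers one calendar year: "Identify all patients with at least one month of dialysis in 2017 (Jan-Dec". Ownership enters through a link to the facility: "Only keep if patient can be linked to a valid facility survey and can be linked to the ownership dataset". No month-varying ownership is described. In Patient Level Regressions, item 3a, the exposure is "Whether patient is dialyzing in a facility that is physician owned (covariate of interest", and item 3b adds "Covariates above (patient, facility, zipcode, temporal characteristics".

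Item 4 covers every patient-level outcome except transfusion and ESA, and its first model is "Logit with patient level fixed effects, non-parametric bootstrap standard errors". The other lines of items 4 to 7 change the link function or the standard error but keep the patient fixed effects. The Subgroup analyses repeat these regressions with LDO ownership and an interaction added.

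Two further entries matter. The covariate list includes "Monthly level fixed effects (an indicator for each month of the year", which shows what the SAP means by a fixed effect. The outcome list includes "Whether patient died in that month", which item 4 does not exempt.

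**The concern.** A patient fixed effect removes anything that is constant within a patient. Ownership of the patient's facility is constant for everyone who stays in one ownership status through 2017. Those patients then add nothing to the ownership coefficient, however many there are.

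The planned estimate becomes a before-and-after contrast in the patients who cross, either by moving or because their facility changes hands. A reader would take it as a comparison of patients in owned and non-owned facilities. People who change facility during a year may differ from those who do not, and may move for reasons tied to the outcome. Patient effects remove stable confounding but not selective moving.

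For death, a patient has at most one event and it ends the record, so the calendar terms predict its timing perfectly.

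**Working it through.** The SAP states no figure on this point, so there is none to reproduce.

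**1. Count of model lines.** Item 4 has 4, item 5b has 4, item 6b has 4, and item 7 has 4 plus 4 under the chain split: 4 + 4 + 4 + 8 = 20. All 20 have patient fixed effects.

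**2. Who informs the ownership coefficient.** After subtracting each patient's own mean, the ownership indicator is exactly 0 in every month for a non-crosser.
- OLS: only crossers contribute.
- Logit: crossers must also change outcome within the year.
- Poisson: crossers must also have at least one non-zero month.

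A simulation confirms this (20,000 patients, 12 months, half in owned facilities, true effect 0.10 in non-crossers and 0 in crossers). With no crossers the fixed-effects coefficient is not estimable. With 1, 3, 5 and 10% crossing, fixed-effects OLS gives -0.012, -0.004, 0.010 and -0.004. Pooled OLS gives 0.086 to 0.100 over 0-10% crossing.

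**3. How much ownership variation is left.** Assume 12 months per patient, one switch at a uniformly distributed month, a share s crossing and a share p in owned facilities. With f the fraction of months in owned status, the within-patient sum of squares for a crosser is 12 × mean of f(1-f) over f = 1/12 to 11/12, which is 12 × 0.1806 = 2.167. The pooled sum of squares per patient is 12p(1-p). The share kept is s × 2.167 / [12p(1-p)].

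| p | 12p(1-p) | s = 1% | s = 5% |
|---|---|---|---|
| 0.2 | 1.92 | 1.13% | 5.64% |
| 0.3 | 2.52 | 0.86% | 4.30% |
| 0.5 | 3.00 | 0.72% | 3.61% |

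If 5-30% of crossers also change outcome (assumption), the share of patients informing the logit is 1% × 5% = 0.05% up to 5% × 30% = 1.5%.

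**4. Subgroup contrasts.** The SAP's two LDO-specific effects are the ownership coefficient alone and its sum with the interaction. In a simulation of 20,000 patients with no ownership crossers and 10% moving between LDO and non-LDO facilities, the within-patient sums of squares are 0 for ownership, 4,408 for LDO and 1,361 for the interaction. The interaction can be estimated without crossers, but neither ownership effect can.

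**5. Death.** In a fixed-effects logit, survivors drop out. A patient who dies in month T contributes -log(Σ exp(-kj), j = 0 to T-1) when the month effects rise with slope k and the other coefficients are 0. With 100,000 simulated patients and an assumed hazard of 1.5% per month, 15,010 deaths fall in months 2-12:

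| k | log-likelihood |
|---|---|
| 0 | -26,862 |
| 1 | -6,553 |
| 2 | -2,151 |
| 5 | -101 |
| 10 | -0.68 |
| 20 | -0.00003 |

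The upper bound is 0, so the likelihood climbs without reaching a finite maximum. A separate run with 20,000 patients shows the same pattern (-5,248 at slope 0, -0.000006 at slope 20). At slope 40 the log-likelihood is 0 for ownership coefficients of -1, 0 and 1 alike, so ownership is not identified. The hazard changes the number of deaths, not this result. Age and years with ESRD also rise over the months and act in the same direction.

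**6. Illustration of selective moving, home dialysis only.** Assume 100,000 patients, 3,000 facilities, 30% owned and no ownership effect on any patient's decision. Patients starting home dialysis move if their facility has no home program. With equal home-program shares (40% in owned and non-owned) the fixed-effects estimate is about 0. With shares of 50/30 or 30/50 it is 7-8 points in absolute size at about 5% crossing and 26-32 points at about 1%. The pooled estimate is about 0 and about 5-6 points in the same settings.

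**The case against.** **A within-patient design is legitimate.** It removes all stable patient confounding, measured or not, which a pooled model cannot do, and its rationale may be in the protocol. This stands as a reason to keep the fixed-effects models. It does not remove the need for the SAP to say which patients its ownership coefficient describes.

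**The models are listed in order, so OLS is available if the logit fails.** Fixed-effects OLS for death (4c, 4d) can indeed be computed. It carries the same patient effects, so it is still a contrast among crossers only.

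**The facility-level regressions compare all facilities.** They do, without patient effects, but their outcomes are "All quality measures from DFC dataset", not the patient-level outcomes.

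**The term may simply mean patient-level covariates.** Sex, race and ethnicity are listed as adjusters although patient indicators would absorb them, which gives this reading some support. Against it, the SAP describes its monthly fixed effects as indicators and enters patient covariates separately in item 3b. If covariates were meant, the wording in all 20 lines needs correcting.

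**The percentages are assumed, and the home-dialysis bias is built in.** Both are true. The share of variation kept also overstates the loss of information, because patients in one facility share its ownership status. In the illustration the pooled model is not at zero either when program shares differ. The conclusion rests on steps 1, 2, 4 and 5, which need none of these rates.

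**Conclusion.** The concern holds and should be fixed before the analysis. As written, the ownership main effect in every patient-level model, and both LDO-specific ownership effects, describe only patients whose ownership status changes in 2017. The two logits listed first for death (4a and 4b) have no finite solution with the specified month indicators. These results follow from the model specification, on the reading that patient fixed effects are patient indicators.

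The size of the loss depends on rates the SAP does not give: 0.7-5.6% of ownership variation kept for 1-5% crossing and 20-50% in owned facilities. The home-dialysis figures depend on the assumed program shares and crossing rates and do not carry over to other outcomes. The absorbed covariates (sex, race, ethnicity) are redundant in these models, not uncontrolled.

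**What to change.** 1. State whether patient-level fixed effects means patient indicators or patient-level covariates. If covariates, correct the wording in items 4-7.
2. If indicators, add for each outcome in items 4-7 and for the LDO repeats: *the same model (logit, OLS or Poisson) without patient fixed effects, adjusted for the listed patient, facility, zipcode and month covariates, with standard errors that allow for clustering by facility and for repeated months per patient.* Movers are not nested in facilities, so two-way clustering by facility and patient is one way to do this.
3. For death in the month, use the pooled logit in place of 4a and 4b.
4. Keep the fixed-effects models where they can be fitted and label them the within-patient (mover) contrast. Report how many patients cross ownership status and how many of those change outcome, and show both estimates side by side.
5. State that sex, race and ethnicity are absorbed in the fixed-effects models.

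The cost is SAP wording and further models on the existing dataset: 12 item-4 outcomes + 3 transfusion definitions + 3 unit definitions + 4 for ESA dose (overall and three splits) = 22, or 44 with the LDO repeats. The pooled models control only measured patient confounding, which is why both estimates should be shown.

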 - iii. Use the number of units of blood detected under Criteria 1. If a blood transfusion detected under Criteria 2 or 3, indicate that the patient received 1 unit of blood. Also include an indicator variable that the patient had a blood transfusion detected under criteria 2 or 3 AND interact this indicator variable with the covariate for whether patient dialyzed in a facility that is physician owned.
 - b. Models

- i. Poisson with patient level fixed effects, non-parametric bootstrap standard errors
 - ii. Poisson with patient level fixed effects, robust standard errors
 - iii. OLS with patient level fixed effects, cluster robust standard errors at facility level
 - iv. OLS with patient level fixed effects, robust standard errors
- 7) Models (in order) for dose of ESA received
 - a. Poisson with patient level fixed effects, non-parametric bootstrap standard errors
 - b. Poisson with patient level fixed effects, robust standard errors
 - a. OLS with patient level fixed effects (dose of ESA received), cluster robust standard errors at facility level
 - i. Include covariate for chain
 - b. OLS with patient level fixed effects (dose of ESA received), robust standard errors
 - i. Include covariate for chain
 - c. Split dataset into 3 separate datasets based on CHAIN of assigned dialysis facility. Specifically, assign each chain to the type of ESA that takes up the majority of all patient-months. Separately, run the following regression on each of the datasets
 - i. Poisson with patient level fixed effects, non-parametric bootstrap standard errors
 - ii. Poisson with patient level fixed effects, robust standard errors
 - iii. OLS with patient level fixed effects (dose of ESA received), cluster robust standard errors at facility level
 - iv. OLS with patient level fixed effects (dose of ESA received), robust standard errors

Subgroup analyses

- 1) Repeat the above regressions, but this time we have the following independent variables of interest (we also include all the other adjusters)
 - a. Whether facility is physician owned (phys_own)
 - b. Whether facility is LDO owned (ldo_own)
 - c. Interaction term between these two (phys_own#ldo_own)
- 2) In addition to reporting the coefficients for these 3 terms, we also care about the following comparisons:
 - a. FOR FACILITIES THAT ARE LDO OWNED: effect of physician ownership
 - i. The parameter of interest is the sum of the following coefficients:
 $\text{phys_own} + \text{phys_own}\#\text{ldo_own}$

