 - b. FOR FACILITIES THAT ARE NOT LDO OWNED: effect of physician ownership
 - i. The parameter of interest is the following coefficient: phys_own
 - c. Use the “lincom” command to estimate the sum and the standard errors of 2ai.

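### OLS models with patient fixed effects cluster on facility only, which splits each mover's linked months between clusters and makes the ownership standard error too small

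*SAP*

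**What the plan says.** In the SAP's Patient Level Regressions, item 4 lists four models in order. The third, 4c, is "OLS with patient level fixed effects, cluster robust standard errors at facility level". The same rule stands in 5b.iii (any transfusion) and 6b.iii (units transfused). For ESA dose, item 7 has "OLS with patient level fixed effects (dose of ESA received), cluster robust standard errors at facility level", both for the whole dataset and within the split by chain (7c.iii). No model is clustered on patient, or on patient and facility together.

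The exposure in item 3a is "Whether patient is dialyzing in a facility that is physician owned (covariate of interest". The data are patient-months, and item 3d of the patient-month dataset selects by the facility of treatment: "Dialyzing in free-standing facility that has fewer than 15% pediatric". Ownership enters through the facility file (Facility level dataset, item 1: "Merge the physician ownership dataset with DFC"), and that file is then merged onto the patient-months (Patient-month level dataset, item 7). No change of ownership during 2017 is described.

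The Subgroup analyses section repeats these regressions with an LDO interaction. Item 2c uses the lincom "command to estimate the sum and the standard errors of 2ai", so that contrast takes its error from whichever model precedes it.

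**The concern.** A patient fixed effect removes everything that is constant within a patient. If ownership is fixed per facility, a patient who stays in one facility has no variation in ownership and adds nothing to the coefficient. The estimate rests on movers, and a mover's months always lie in at least two facility clusters. Demeaning by patient forces that patient's residuals to sum to zero, so the months before and after the move are linked by construction, even without serial correlation. Facility-only clustering assumes that they are unrelated.

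Facility-clustered OLS is the only patient-level model for which the SAP names a cluster unit. If its standard error is too small, its intervals for the covariate of interest are too narrow across all patient-level outcomes, and the LDO contrast repeats the error when lincom follows one of these fits.

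**Working it through.** The SAP states no standard error, power, mover share, move timing or correlation, so there is no figure of its own to reproduce. The check takes up to T = 12 months per patient (January to December 2017) and two premises read from the text: facility is the one attended that month, and ownership does not change within a facility.

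**Algebra for a patient with one move.** Let f be the share of months after the move, which is taken to be into an owned facility. Demeaned ownership is −f before the move and 1 − f after it. Let R be the sum of the demeaned residuals after the move; the sum before is then −R.

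- Score before: (−f)(−R) = fR. Score after: (1 − f)R. Total: R.
- Correct variance contribution: R².
- Contribution under facility clustering: f²R² + (1 − f)²R² = [1 − 2f(1 − f)]R².
- Dropped term: 2f(1 − f)R², which cannot be negative under pure patient demeaning. A move in the other direction gives the same result.

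The SE ratio is the square root of the share kept, and the type I error is 2[1 − Φ(1.96 × SE ratio)].

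| Split of 12 months | Share kept | SE ratio | Type I error |
|---|---|---|---|
| 1/11 | 0.847 | 0.92 | 7.1% |
| 2/10 | 0.722 | 0.85 | 9.6% |
| 3/9 | 0.625 | 0.79 | 12.1% |
| 4/8 | 0.556 | 0.75 | 14.4% |
| 5/7 | 0.514 | 0.72 | 16.0% |
| 6/6 | 0.500 | 0.71 | 16.6% |

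With m the number of months on one side of the move, m uniform over 1 to 11 and independent months, each m is weighted by m(12 − m). The weights sum to 286 and their squares to 8,294, so the share kept is 1 − (2/144)(8,294/286) = 1 − 58/144 = 0.597. The SE ratio is 0.77 (0.81 with a 12/11 degrees-of-freedom factor) and the type I error is about 13%.

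**Simulation, all inputs assumed.** The grid has 36 cells of 2,000 replicates: 600 or 3,000 movers; 300 or 3,000 facilities; AR(1) month correlation 0, 0.5 or 0.8; facility-effect SD 0, 0.1 or 0.2 of the month-level SD; 30% owned; uniform move month; no true effect. The facility-only ranges cover results with and without the 12/11 factor.

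| Facility-effect SD | Facility-only SE / true SD | False positives | Two-way SE / true SD | False positives |
|---|---|---|---|---|
| 0 | 0.74–0.81 | 11–15% | 0.97–1.01 | 4.6–5.7% |
| 0.1 | 0.65–0.79 | 12–20% | 0.79–1.00 | 5–12% |
| 0.2 | 0.57–0.79 | 12–26% | 0.64–0.99 | 6–20% |

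The two-way error was the larger in all 36 cells. Further runs of the facility-only error:

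- Timing (600 movers, no facility effects): 1/11 split 0.92–0.98 and 5–7%; 3/9 split 0.78–0.84 and 10–13%; 6/6 split 0.70–0.74 and 15–17%.
- Binary outcome at 10% or 30% prevalence, uniform timing: 0.74–0.81 and 11–15%.
- LDO contrast (1,500 movers, 1,500 stayers, 300 facilities, month effects, 60% LDO): the lincom sum gave 0.72–0.81 and 12–16%; two-way gave 0.94–1.01 and 4.5–7%.
- A separate simulation (400 facilities, 6,000 patients, 2–30% movers, month effects, 300 replicates): 0.69–0.89 and 10–21% in the scenarios where movers alone identify the effect.

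**The case against.** **Open premises.** Item 7c speaks of an assigned facility ("Split dataset into 3 separate datasets based on CHAIN of assigned dialysis facility"), and the facility-level dataset has a plurality rule ("If a patient has multiple facilities, assign that patient to the facility that holds the plurality share"). If one facility were fixed per patient for the year, the argument would not apply. But the patient effect would then absorb ownership and leave no coefficient to estimate, so the monthly reading is the natural one. Ownership fixed within a facility is inferred from the merge. If 10% of facilities changed ownership during the year, the bias would shrink: one simulation gave a ratio of 0.97–0.98 with 4–7% rejection, another 0.89 with 9%. The SAP describes no such change.

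**Month effects.** The month indicators make the sign of the dropped term only approximate. It was negative for roughly 3–14% of two-facility movers in a check with month effects. With three facilities (not owned, owned, not owned; 4/4/4 months) it can also take either sign, although with independent months the expected share kept is 0.67. The average direction survives both.

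**Reach.** These are third-listed models, after two logit or Poisson models. This limit stands: nothing here sizes an error in the first-listed results.

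**The adjacent robust line.** If robust meant clustered by patient, the next model would already be adequate without facility effects (0.99–1.00, 3–4% rejection). The SAP does not define it. Read as heteroskedasticity-only, the ratio was 0.40–0.79 under positive serial correlation or a facility effect.

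**Assumed sizes and a partial remedy.** Both stand. Timing drives the size, and two-way clustering still falls short where many movers share few facilities with strong effects.

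**Conclusion.** The concern holds. As written, the OLS models pair patient fixed effects with a cluster unit that separates the months through which ownership is estimated, and the resulting standard error is too small on average. This rests on monthly facility assignment and on ownership being largely fixed within a facility over 2017.

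The size cannot be taken from the SAP. Even move timing without facility effects gives a standard error about a fifth to a quarter too small and 11–15% rejection at nominal 5%. Facility effects make it worse, and very short stays elsewhere make it minor. It should be fixed before analysis, but it concerns one of several listed standard errors and not the first-listed inference. Confidence in the size is moderate.

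**What to change.** 1. In 4c, 5b.iii, 6b.iii, the facility-clustered OLS lines of item 7 (including 7c.iii) and their subgroup and lincom repeats, specify standard errors two-way clustered by patient and facility.
2. State that facility in the patient-month dataset is the one attended in that month, and reconcile this with the wording of 7c.
3. Note that two-way clustering can still be too small when facility effects are large and many movers share few facilities. The worst cells were 3,000 movers in 300 facilities.

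Two clarifications, not corrections: keep the robust lines of the patient-level models and define robust there as clustered by patient; and state that the bootstrap resamples whole patients with all their months. Neither accounts for correlation within facilities: with a very strong facility effect, patient-only clustering gave 0.71 and 19% rejection.

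Optionally, report how many patients change ownership type, how their months split and how many facilities they use, since these set the size of the error.

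The cost is SAP wording and one standard-error option; no new data are needed. OLS intervals widen. With uniform timing, the two-way error exceeds the facility-only error by 24–32% without facility effects and by 8–32% with them. Without facility effects, the increase is 4–9% for a 1/11 split and 36–42% for a 6/6 split.

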 (<https://qualitynet.cms.gov/inpatient/measures/readmission/resources#tab3>, “2018 All-Cause Hospital Wide Measure Updates and Specifications Report Hospital-Level 30-Day Risk-Standardized Readmission Measure – Version 7.0”, pages 51 and 68)
 - v. Whether patient had a blood transfusion that month
 - 1. Criteria 1
 - a. From inpatient, outpatient, SNF claims
 - b. Revenue code 0390 OR 0392 OR 0399 PLUS any of the following HCPCS/CPT
 - i. P9010
 - ii. P9011
 - iii. P9016
 - iv. P9021
 - v. P9022
 - vi. P9038
 - vii. P9039
 - viii. P9040
 - ix. P9051
 - x. P9054
 - xi. P9056
 - xii. P9057
 - xiii. P9058
 - c. Calculate number of units of blood by taking the sum of the units for (Revenue center code 0390 OR 0392 OR 0399) across all line items that correspond to that specific day.
 - i. Sum across all days for a given month
 - 2. Criteria 2
 - a. If Criteria 1 is missing, then determine whether a blood transfusion occurred for the entire claim (assign to the month of the through date of the claim)
 - b. Look for value code 37
 - 3. Criteria 3

- a. If Criteria 1 is missing, then determine whether a blood transfusion occurred for the entire claim (assign to the month of the through date of the claim)
- b. Look for any of the following ICD procedure codes:
 - i. ICD9
 - 1. 9903
 - 2. 9904
 - ii. ICD10
 - 1. 30230H1, -P1, -N1
 - 2. 30233H1, -P1, -N1
 - 3. 30240H1, -P1, -N1
 - 4. 30243H1, -P1, -N1
 - 5. 30250H1, -P1, -N1
 - 6. 30253H1, -P1, -N1
 - 7. 30260H1, -P1, -N1
 - 8. 30263H1, -P1, -N1
- vi. Whether a patient received an ESA and their dose (using CROWNWeb data)
 - 1. Consolidate to Darbepoetin, Erythropoietin alfa, Erythropoietin beta
 - 2. Make sure units are consistent (darbe in mcg, Epo alfa in units, Epo beta in units)
 - 3. Make sure the doses are normalized, to the same mean (i.e., we want to make sure we are looking at relative changes in doses within the same ESA)
 - a. Take the mean doses of each of the ESA types, then divide all the doses by this mean. In other words, all means will be set at “1”
 - 4. For each month of dialysis create the following variables
 - a. Whether ESA administered
 - b. Type of ESA administered
 - c. Dose
 - 5. For each dialysis chain, determine the ESA that is the majority of patient-months

ANALYSES

Facility Level Outcomes

- 1) Use facility level dataset (patient level covariates are collapsed to facility level using summary statistics for that facility)
- 2) Dependent variable (left hand side)

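### The chain covariate is specified for the pooled OLS models of ESA dose but not for the pooled Poisson models listed ahead of them, so the four models differ in adjustment as well as in form

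*SAP*

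**What the plan says.** SAP, Patient Level Regressions, item 7 is headed "Models (in order) for dose of ESA received". Its entries are, in sequence:

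- Two pooled Poisson models. The first is "Poisson with patient level fixed effects, non-parametric bootstrap standard errors" and the second is the same model with robust standard errors. Neither has a sub-item.
- Two pooled OLS models. The first is "OLS with patient level fixed effects (dose of ESA received), cluster robust standard errors at facility level" and the second uses robust standard errors. Each has the sub-item "Include covariate for chain".
- A split analysis, "Split dataset into 3 separate datasets based on CHAIN of assigned dialysis facility", in which each chain is classed by its predominant ESA and Poisson and OLS models are fitted in each part.

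Two other places bear on what chain means. Item 3b of the same section puts "Covariates above (patient, facility, zipcode, temporal characteristics") into every patient-level regression, and the facility part of that list contains "Chain vs. independent". The ESA data items ask for the predominant ESA of each dialysis chain, which needs the chain's identity. On dose scaling the SAP says: "Take the mean doses of each of the ESA types, then divide all the doses by this mean".

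**The concern.** Models listed in order for one outcome are normally read against each other: if Poisson and OLS disagree, the reader looks to the functional form or the standard errors. Here a disagreement could also come from the chain term, and the plan gives no way to tell these apart.

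The chain term could matter because of how the ownership effect is identified. With patient fixed effects, a patient whose ownership exposure never changes contributes nothing to the ownership coefficient. The data cover the months of 2017 and ownership is merged on as a facility attribute, so the coefficient comes essentially from patients who change facility. If such a move also takes the patient from one chain to another, and the two chains dose differently, a model without chain identity can attribute part of the chain difference to ownership. The models placed first would be the exposed ones.

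**Working it through.** **Text comparison.** The SAP states no figure on this point, so there is none to reproduce. For the pooled dose models:

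| Pooled model in item 7 | Patient fixed effects | Chain vs. independent (item 3b) | Separate chain line |
|---|---|---|---|
| Poisson, bootstrap SE | yes | yes | no |
| Poisson, robust SE | yes | yes | no |
| OLS, facility-clustered SE | yes | yes | yes |
| OLS, robust SE | yes | yes | yes |

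If the separate line meant the binary chain-versus-independent term, it would add nothing, since item 3b already supplies that term. The OLS models in items 4, 5 and 6 rely on the same item 3b and carry no such line; it appears only for ESA dose. In the ESA material chain is used for the particular chain (the predominant-ESA step and the split in item 7). The line therefore reads most naturally as chain identity.

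**Illustrative size.** All inputs below are assumptions; none comes from the SAP.

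- 200,000 patients, two periods, true ownership dose ratio 1.00.
- Three facility groups of equal size: chain A, chain B and independents. The group is drawn afresh in each period, so 1 − 3 × (1/3)² = 2/3 of patients change group.
- Chain B doses at G times the level of A and of independents, with G = 1.1, 1.25 or 1.5. This is the gap that remains after dose scaling.
- Physician-owned share 0.5 − s/2 in A, 0.5 + s/2 in B and 0.5 in independents, with s = 0, 0.2 or 0.4. At s = 0.4 the shares are 0.3 and 0.7.
- Gamma-distributed patient level and gamma dose noise.

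The two-period Poisson model with patient fixed effects was fitted by maximising Σ[y₂η − (y₁ + y₂) log(1 + e^η)], where y₁ and y₂ are the patient's two doses and η = β·Δ(owned) + γ·Δ(chain vs. independent). Chain identity adds δ·Δ(chain B). The estimated ownership ratio is exp(β):

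| G | s | No chain identity | Moves only within one chain, no chain identity | Chain identity added |
|---|---|---|---|---|
| 1.1 | 0 | 1.002 | 1.002 | 1.003 |
| 1.1 | 0.2 | 1.015 | 0.998 | 0.999 |
| 1.1 | 0.4 | 1.026 | 1.005 | 1.004 |
| 1.25 | 0 | 1.002 | 1.003 | 1.001 |
| 1.25 | 0.2 | 1.030 | 0.996 | 1.004 |
| 1.25 | 0.4 | 1.061 | 1.001 | 1.001 |
| 1.5 | 0 | 0.997 | 1.002 | 0.998 |
| 1.5 | 0.2 | 1.058 | 0.995 | 1.006 |
| 1.5 | 0.4 | 1.119 | 0.996 | 0.998 |

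Each cell is one simulated dataset. Cells where the method should return 1.00 lie between 0.995 and 1.006, so departures of that order are noise. Without chain identity the false ratio runs from about 1.00 to 1.12. It is nil when ownership is unrelated to chain (s = 0) and when moves stay within a chain. Adding chain identity brings every scenario back to 0.998 to 1.006.

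**The case against.** A reader might infer that the first-listed dose estimate is confounded by chain practice, or that the Poisson models have no chain adjustment at all. The SAP supports neither. Bias needs patients who change chain and ownership together, an association between ownership and chain, and a dosing gap left after the existing adjustments; the document gives no data on any of these. Several safeguards also apply to the Poisson models:

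- *Chain versus independent* is in every model. This stands, but it does not separate one chain from another.
- *Patient fixed effects* remove chain differences for patients who stay put. True, but those patients carry little or no information on ownership.
- *Scaling by ESA type* removes much of the gap between chains that use different agents. This stands. It leaves gaps between chains that use the same agent.
- *The split analysis* repeats the Poisson models in sets of chains grouped by predominant ESA. This limits differences across agents, but several chains can share a set and no chain line is given there.
- *The subgroup models* add an LDO indicator and its interaction with ownership. That is a further term for chain type, coarser than identity, and these models repeat item 7 with its mismatch.

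It is also fair that the SAP says only that the models are in order. It does not call Poisson primary, and calling it the preferred model goes beyond the text. The chain-identity reading is likewise an inference, since outline plans often repeat themselves. The lettering of item 7 (a, b, a, b, c) may mean that the Poisson lines were placed above an existing OLS list and the sub-item was not carried over, or it may be a formatting artefact. If it was a slip, the written plan still specifies different adjustment for the four models and still leaves the covariate undefined.

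**Conclusion.** The inconsistency stands on the text alone: two of the four pooled dose models carry a chain covariate, the two listed first do not, and no reason is given. Read as chain identity, this means that the models do not estimate the same adjusted effect, and that the first-listed ones are not protected against a source of confounding that the later ones adjust for.

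Confounding itself is a possibility, not a finding. The range of about 1.00 to 1.12 rests wholly on assumed dose gaps, ownership shares and frequent moves between chains. It is neither an estimate for these data nor an upper limit, and it shrinks to nothing if moves stay within chains or ownership is unrelated to chain. The point concerns one outcome among many and is worth correcting mainly because the correction is cheap.

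**What to change.** In item 7, give both pooled Poisson models the same chain sub-item as the two pooled OLS models. State that it means chain identity, as the ESA items imply, and not the chain-versus-independent term already in every model. If the difference between Poisson and OLS is intended, say so and give the reason.

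The cost is about one line of SAP text, a few more parameters and a small loss of precision. Two consequences should be noted when drafting. With independents as the reference level, the chain indicators absorb the chain-versus-independent term. If LDO status follows from chain, they also absorb the LDO main effect in the subgroup dose models, while the ownership term and its interaction with LDO can still be estimated. On this reading, both already apply to the pooled OLS models.
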